8.6 METHODS FOR STATISTICAL ANALYSIS

8.6.1 Analysis of Baseline Parameters

Descriptive summary statistics (n, mean, standard deviation (SD), median, minimum, maximum) or frequency counts of demographic and baseline data (age, sex, education, marital status, time since diagnosis of RRMS, severity of disease (EDSS), concomitant medications, HRQoL, depression/anxiety and fatigue scores) will be presented by treatment group and overall for the ITT and PP populations (no statistical test will be performed).

8.6.2 Analysis of Primary Endpoint

The primary endpoint will be analyzed using a linear mixed model with the change from baseline to month 6 and month 12 as dependent variable and group, time and baseline value of the dependent variable as fixed factors. The patient specific intercept will be included as a random factor. The difference between groups at month 6 and month 12 will be presented along with 95 % confidence intervals. The 12 month is the primary endpoint.

The derivation from the 9 questions to the MSIS-29 psychological scale can be performed using the following equation:

$$\text{Score (0-100)} = (\sum(9 \text{ questions}) - 9) / 0.36$$

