8.3 ENDPOINTS

8.3.1 Primary Endpoint

MSIS-29 psychological scale (9 questions): Change from baseline to month 12.

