8.3.2 Secondary Endpoints

- MSIS-29 psychological scale (9 questions): Change from baseline to month 6
- MSIS-29, full scale: Change from baseline to months 6 and 12
- EQ5D-5L: Change from baseline to months 6 and 12
- Adherence: Proportion of patients with <10% missed injections during 6 and 12 months, measured with the software RDS 2.0
- FSS and MFIS: Change from baseline to months 6 and 12
- HADS: Change from baseline to months 6 and 12
- Working ability: Change from baseline to month 12 will be assessed by recording the following information per patient:
 - I am employed/have my own company
 - 1a. My employment is based on hours/week _____
I work my normal working hours (Y/N)
 - 1b. I now work hours/week _____
 - 1c. For the rest of the time I receive (sickness, activity compensation, parental compensation)
 - I study (indicate how much)
 - I have full sickness (full disability pension)
 - I have retirement
 - None of the above applies to me
- AEs: Proportion of patients with reported AEs at month 12

- Patients satisfaction:
The following question will be answered at the 12 months visit and recorded in the eCRF: “How satisfied are you with the overall treatment and support from health care providers during the last 12 months?”
Categorized as follows: Very unsatisfied / Unsatisfied / Satisfied / Very satisfied
Please specify: _____

- HC Personnel satisfaction:
The following question will be answered once per site at the 12 months visit for the last patient at the site and recorded in the eCRF: “How satisfied are you with the overall treatment and support from health care providers during the last 12 months?”
Categorized as follows: Very unsatisfied / Unsatisfied / Satisfied / Very satisfied
Please specify: _____

- Lifestyle questionnaire: Change from baseline to month 6 and 12 (arm 2)

- Lifestyle goals:
The following questions will be included in the questionnaires completed by the patients before the 12 months visit (arm 2):
 - Was the goal achieved? (Y/N)
 - If yes, better than expected or achieved as expected?
 - If better than expected, a lot or a little better than expected?
 - If no, a little or a lot less than expected?

- Health economy based on QoL and working ability at 12 months

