8.6.3 Analysis of Secondary Endpoints

Numeric secondary endpoints will be analyzed using the same method as for the primary endpoint. Dichotomized endpoints (e.g. proportion of patients meeting the criteria for adherence) will be analyzed at month 6 and month 12 separately using a logistic regression. The results will be presented as odds ratios with 95 % confidence intervals.

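### The primary mixed model has no group-by-time term, so it gives one group difference averaged over months 6 and 12 instead of the month-12 effect that is the primary endpoint

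*Protocol*

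**What the plan says.** Section 8.6.2 specifies "a linear mixed model with the change from baseline to month 6 and month 12 as dependent variable". The fixed part is "group, time and baseline value of the dependent variable as fixed factors", and "The patient specific intercept will be included as a random factor". No group-by-time term is named there, in the synopsis (which repeats the paragraph) or anywhere else in the protocol.

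The same paragraph then promises visit-specific results: "The difference between groups at month 6 and month 12 will be presented along with 95 % confidence intervals". It adds: "The 12 month is the primary endpoint".

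The endpoint sections keep the two visits apart. Section 8.3.1 makes the primary endpoint "MSIS-29 psychological scale (9 questions): Change from baseline to month 12". Section 8.3.2 lists as secondary "MSIS-29 psychological scale (9 questions): Change from baseline to month 6".

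Section 8.6.3 carries the model over: "Numeric secondary endpoints will be analyzed using the same method as for the primary endpoint".

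**The concern.** With only a main effect of group, the fitted difference between arms is the same at every visit. The month-6 and month-12 differences, and their confidence intervals, would be identical, and neither would be specific to its visit. The primary endpoint and the first secondary endpoint would not be estimated separately. The full MSIS-29, EQ5D-5L, FSS, MFIS and HADS, which are also measured at both visits, inherit the problem.

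This matters because an equal effect at both visits cannot be presumed. The call schedule in section 6.1 concentrates contacts in the first five months and continues with calls in months 8, 9 and 11, so growth and fading are both plausible. If the effect grows, the month-12 effect is underestimated and power can fall below the planned 80%. If it fades, a month-6 benefit can be reported as a month-12 benefit that no longer exists.

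A lesser point is the covariance. A random intercept with a single residual variance imposes the same variance at both visits, so the month-12 interval would use a variance pooled over both.

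**Working it through.** **Inputs from the protocol (section 8.1).** Difference 14 points, SD 25, 104 evaluable patients randomised 1:1 (52 per arm), 80% power, 5% significance level, 20% drop-out, 130 included.

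**Assumed, because the protocol does not give them.** The month-6 effect d6; the correlation ρ between the two changes (0.6, range 0.4 to 0.8); SD 25 at both visits. Effects are written as benefit for Arm 2.

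**Step 1: the plan's own figure.** A two-sided two-sample t-test with standardised difference 14/25 = 0.56 needs 51.03 per arm, so 52 per arm or 104 in total, with power 80.7%. Then 104/0.8 = 130. The sample size reproduces, and it is a calculation for a comparison at one time point.

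**Step 2: what the listed model estimates.** With complete data and a random intercept, the group coefficient is the arm difference in each patient's mean of the two changes:

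- estimate = (d6 + d12)/2
- SE = 25 × √((1+ρ)/2) × √(2/52)

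For ρ = 0.6, SE = 25 × 0.894 × 0.196 = 4.39. The month-12 contrast has SE = 25 × 0.196 = 4.90.

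**Step 3: consequences (52 per arm, complete data, two-sided 5%).**

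| True effect at months 6, 12 | Listed model estimates | Rejection rate, ρ = 0.6 (ρ = 0.8 to 0.4) | Rejection rate of month-12 contrast |
|---|---|---|---|
| 7, 14 | 10.5 | 66% (61–72%) | 81% |
| 0, 14 | 7 | 35% (32–39%) | 81% |
| 14, 14 | 14 | 89% (85–92%) | 81% |
| 10, 0 | 5 | 20% (19–23%) | 5% |

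In the first row the bias is 10.5 − 14 = −3.5 points, or 0.8 SE, so the 95% interval covers the true month-12 effect only 87–88% of the time.

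**Step 4: break-even.** At ρ = 0.6 the listed model keeps the planned power if its estimate is at least 14 × 0.894 = 12.5, that is, if d6 ≥ 2 × 12.5 − 14 = 11. A mild build-up therefore does not cost power, although the month-12 effect is still underestimated.

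**Step 5: simulation with drop-out.** Both models were fitted to simulated trials of 65 per arm with 20% of month-12 values missing, in sets of a few hundred trials. For (7, 14) the listed model averaged 9.7 to 10.2 across sets, and the model with the interaction gave 13.7 to 14.4 at month 12. For (10, 0) the listed model rejected in 30–34% of trials, against 4–4.5% with the interaction. These rates exceed the 20% in the table because the design differs: all 65 per arm contribute at month 6, and missing month-12 values shift weight towards month 6.

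**Step 6: variance pooling (illustration only).** If the SD were 22 at month 6 and 28 at month 12, the pooled SD would be √((22² + 28²)/2) = 25.2. Since 25.2/28 = 0.90, the month-12 SE would be about 10% too small.

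**The case against.** The strongest reply is that the intent is clear. The paragraph promises a difference at each visit and names month 12 as primary, so the listed terms may be shorthand, and section 8 leaves details to a separate SAP. An interaction was probably intended. But the protocol itself names the fixed and random terms of its primary analysis, and those terms cannot deliver the promised contrasts. An SAP that follows them inherits the error, and one that adds the interaction departs from the protocol text.

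The size rests on assumed trajectories. That is true. With a constant effect the listed model is unbiased and more powerful (89% against 81%), and the call schedule does not favour a late-building effect. The protocol, however, nowhere assumes a constant effect, and it treats the two visits as different endpoints.

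Two limits on scope stand. A random intercept is a standard choice for two visits, and the SDs of 22 and 28 are not in the protocol, so the covariance point is secondary. Working ability is recorded only at baseline and month 12, and dichotomised endpoints are analysed by visit, so the averaging affects neither.

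**Conclusion.** The concern holds. That the listed model has only one group coefficient is algebra and needs no assumption: as written, it cannot produce the month-12 difference as a separate quantity, and section 8.6.2 contradicts itself. How much harm follows depends on the unknown month-6 effect and on the correlation. The harm ranges from none when the effect is constant, through a loss of about 15 percentage points of power when half the effect is present at month 6, to a false month-12 claim in about one trial in five when a 10-point benefit fades completely, and more often with month-12 drop-out. Because the primary estimate, its interval and its error rate all depend on this specification, it must be corrected before the analysis. The sample size is not in error.

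**What to change.** In section 8.6.2 and in the statistical methods of the synopsis, list the fixed effects as group, time (categorical), group-by-time, baseline score and baseline-by-time, with an unstructured covariance for the two visits in place of the random intercept. State that the primary test is the month-12 group contrast from this model and that the month-6 contrast is secondary. In section 8.6.3, apply the same model to the numeric secondary endpoints measured at both visits.

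The group-by-time term and the named month-12 contrast are essential. Baseline-by-time and the unstructured covariance are sensible additions that remove the equal-variance restriction.

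The cost is a sentence of text. No new data are needed, and the 104 evaluable and 130 included patients stand, because they were calculated for a comparison at one time point. If the effect is truly constant, the SE rises from about 4.4 to 4.9 points at correlation 0.6, which returns power to the planned 81%.

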8.6.3 Analysis of Secondary Endpoints

Numeric secondary endpoints will be analyzed using the same method as for the primary endpoint. Dichotomized endpoints (e.g. proportion of patients meeting the criteria for adherence) will be analyzed at month 6 and month 12 separately using a logistic regression. The results will be presented as odds ratios with 95 % confidence intervals.

8.6.4 Safety Analysis

Data on AEs will be collected at scheduled and unscheduled visits, based on information spontaneously provided by the patient.

Summary tables of incidence and observed number of treatment emergent AEs will be presented by study arm and sorted by system organ class (SOC) and by preferred term (PT). Summary tables will be presented for (1) all AEs, (2) all AEs by severity and (3) all serious AEs.

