4 TRIAL OBJECTIVES

Primary objective

To assess the impact of the patient support program MSP on HRQoL at 12 months, using the psychological scale of MSIS-29, in patients administered Rebif with the RebiSmart device compared to patients only receiving technical support for RebiSmart.

Secondary objectives

1. To assess the impact of the patient support program MSP on:

- HRQoL
 - MSIS-29, psychological scale at 6 months
 - MSIS-29, full scale at 6 and 12 months
 - EQ5D-5L at 6 and 12 months
- Adherence at 6 and 12 months
- Fatigue (FSS, MFIS) at 6 and 12 months
- Depression and Anxiety (HADS) at 6 and 12 months
- Working ability at 12 months
- The number of reported adverse events at 12 months
- Patient satisfaction at 12 months
- Health care personnel satisfaction at 12 months
- Lifestyle goals at 12 months
- Health economy based on QoL and working ability at 12 months

2. To describe the impact of MSP in the following sub groups:

- Males and females
- Educational level
- According to severity of MS symptoms (EDSS) at baseline, patients with EDSS > 4.0 vs. ≤ 4.0

[figure not shown]
- According to impairment in HRQoL at baseline
- Patients with at least one lifestyle problem at baseline according to the lifestyle questionnaire

3. To describe baseline characteristics and concomitant therapies

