6 INVESTIGATIONAL PATIENT SUPPORT PROGRAM AND OTHER TREATMENTS IN THE TRIAL

6.1 DESCRIPTION OF INVESTIGATIONAL PATIENT SUPPORT PROGRAM (MINSUPPORT PLUS)

MSP is a service from Merck AB which includes:

- Technical support for the RebiSmart device
- Personal coaching regarding treatment and understanding of the disease
- Lifestyle Guide
- Web support (personal health records)

The patient is assigned a personal nurse/coach and a personal health counselor/advisor. The first two services described below are performed by the personal nurse and the third service by the personal health counselor.

1. Technical support

The personal nurse provides technical support for the RebiSmart device.

2. Treatment and understanding of the disease

The personal nurse supports and guides the patient in adherence to the prescribed Rebif® therapy, provides disease information and motivating support for the treatment of MS. The nurse checks the patient's understanding of the doctor's prescription, the administration of the medicine and makes continuous evaluation of patient's status, issues, and problems with regard to treatment using a set of questions in the patient's health record ("Hälsojournal").

This support is managed by;

- A set of telephone contacts with the patient; 1 registration call followed by 6 motivational calls during 12 months. The calls to the patients are booked 1-7 days in advance
- The telephone calls are supported by customized mailings and mobile text messaging to the patients

4. Lifestyle Guide

This support is provided by a personal health counselor. The purpose of the Lifestyle Guide is to inspire and motivate a choice of lifestyle(s) in order to improve health and wellbeing. The Lifestyle Guide is based on The Swedish National Board of Health and Welfare's National Guidelines for Methods of Preventing Disease. These guidelines provide recommendations for methods of preventing disease by supporting patients in their efforts to change an unhealthy lifestyle habit. The Lifestyle Guide offers guidance in six areas; diet, exercise, stress management, smoking, sleep and alcohol. Counselling is individual, which means that the patient agrees with the lifestyle counsellor which areas to focus on and in which order. Most people who start with lifestyle changes will end in 6-10 weeks (30). As our intention is to achieve long term change, the program runs during 12 months.

The Lifestyle Guide is managed by;

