7.3 ASSESSMENT OF SAFETY

7.3.1 Management and reporting of Adverse Events

Adverse events will be documented during the whole observational period, starting at the baseline visit, after signing of the informed consent form by the patient (both conditions must be met). Recording of adverse events stops when the Investigator signs off the eCRF at Month 12 or during an early discontinuation visit.

Definitions

Adverse Event:

An adverse event (AE) is any untoward medical occurrence in a patient or a clinical trial subject, administered a pharmaceutical product, which does not necessarily have a causal relationship with this treatment. An AE can therefore be any unfavorable and unintended sign (including an abnormal laboratory finding), symptom, or disease temporally associated with the use of a medicinal product, whether or not considered related to the medicinal product.

In cases of surgical or diagnostic procedures, the condition/illness leading to such a procedure is considered as the AE rather than the procedure itself.

In case of a fatality, the cause of death is considered as the AE, and the death is considered as its OUTCOME.

The Investigator is required to grade the severity/intensity of each adverse event.

Adverse Drug Reaction (ADR):

A response to a medicinal product which is noxious and unintended. Response in this context means that a causal relationship between a medicinal product and an adverse event is at least a reasonable possibility. Adverse reactions may arise from use of the product within or outside the terms of the marketing authorisation or from occupational exposure. Conditions of use outside the marketing authorisation include off-label use, overdose, misuse, abuse and medication errors.

Serious Adverse Event:

- Results in death.
- Is life-threatening at time of event.
- Requires in-patient hospitalization or prolongation of existing hospitalization.
- Results in persistent or significant disability/incapacity.
- Is a congenital anomaly/birth defect.
- Is otherwise considered as medically important.

Severity of an Adverse Event:

Investigators must assess the severity/intensity of Adverse Events according to the Qualitative Toxicity Scale, as follows:

Mild: The patient is aware of the event or symptom, but the event of symptom is easily tolerated.

Moderate: The patient experiences sufficient discomfort to interfere with or reduce his or her usual level of activity.

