7.3.3 Expedited Reporting of Adverse Events

The Investigator must notify the Sponsor WITHIN 24 HOURS of awareness of a new Adverse Event or of new information on a previously reported Adverse Event (= "follow-up").

To do so, the Investigator must complete the adverse event section of the eCRF.

If the event is non-serious an electronic notification will be sent to the Sponsor's Local Drug Safety department automatically, who will extract relevant data for reporting.

If the event is serious, the Investigator must also complete the Sponsor Serious Adverse Event Report Form/Fax template located in the eCRF, follow the eCRF's completion instructions, and fax it directly to the Sponsor's Local Drug Safety department. Reporting by e-mail is also possible.

[contact]

Email address: [contact]

For any new Adverse Event, the following minimum information is required as initial notification:

- Investigator name and contact details;
- Patient identification (study number, patient number, sex, age, ...);
- Merck Drug(s);
- Description of Adverse Event.
- Assessment of the causal relationship of AEs to Rebif

Note: the Fax template found in the eCRF is a standard form for reporting Serious Adverse Events. Its fields will not fully reflect all study designs and situations. Information should be provided based on what can be found in the eCRF (i.e., the RebiQoL protocol number + site number + patient number in the "patient ID" field, even if the number format does not perfectly match), as well as anything deemed important, rather than too strictly trying to follow the format of the reporting form.

When information is communicated via telephone, a written report must be sent immediately thereafter by fax or e-mail, again using the Fax template found in the eCRF. If some data are missing, the form has to be completed with the available data and a follow-up report must be sent as soon as possible.

The Investigator/Reporter must respond to any request for follow-up information or questions the Sponsor may have regarding the AE within the same timelines as for initial reports.

Serious Adverse Drug Reactions will be expedited by the Sponsor to Competent Health Authorities according to local regulations, which usually require a maximum period of 15 days. Non-serious Adverse Drug Reactions will be expedited by the Sponsor to Competent Authorities according to local regulations, which usually require a maximum period of 90 days.

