8.3.3 Safety Endpoints

Any adverse event will be recorded by the nurse at visit 2 (12 months). The proportion of patients with adverse events reported will be compared between the two study arms.

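### Arms are compared on spontaneously reported AEs although only Arm 2 has scheduled support calls, so reporting may differ between arms in either direction; the AE capture and measure wording also needs aligning.

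*Protocol*

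**What the plan says.** **How AEs are collected and compared.** Section 8.6.4 states: "Data on AEs will be collected at scheduled and unscheduled visits, based on information spontaneously provided by the patient". Section 8.3.2 lists the proportion of patients with AEs as a secondary endpoint, and 8.3.3 adds: "The proportion of patients with adverse events reported will be compared between the two study arms". Section 8.6.3 gives dichotomized endpoints a logistic regression with odds ratios and 95% confidence intervals, at months 6 and 12 separately.

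**When AEs are captured.**
- Section 7.3.1: "Adverse events will be documented during the whole observational period, starting at the baseline visit".
- Section 7.3.3: "The Investigator must notify the Sponsor WITHIN 24 HOURS of awareness of a new Adverse Event".
- Section 8.3.3 says only "Any adverse event will be recorded by the nurse at visit 2 (12 months").
- The schedule in 7.1.1 marks AEs at month 12 alone.

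**Which measure.** The secondary objective in Section 4 is "The number of reported adverse events at 12 months". The endpoint lists in 7.2 and 8.3.2 give the proportion of patients.

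**Contact by arm.** Section 6.1 schedules one registration call and six motivational calls by the personal nurse, and six conversations with the health counselor. The nurse continuously evaluates "issues, and problems with regard to treatment using a set of questions in the" patient's health record. All calls are logged in the vendor's records. Arm 1 receives technical support, with no contact schedule stated.

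**The concern.** A comparison of reported AEs is fair only if patients in both arms are equally likely to have an event put on record. Here the clinic relies on what patients volunteer, while one arm also has regular conversations in which a nurse asks about treatment problems. Two mechanisms follow, and the protocol governs neither:

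- Calls may make Arm 2 patients more aware of events and more likely to mention them at the clinic, or the vendor may pass events on. Either would raise the recorded proportion in Arm 2.
- Arm 2 patients may tell the coach and then not repeat it to the clinic. That would lower it.

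This matters for the trial's own argument. Section 3 describes AEs as a major barrier to adherence and stresses managing them, so a real reduction under MSP would be a result of interest. Unequal reporting could hide such a reduction, imitate one, or produce an apparent excess. If the data are collected without a common question and without a source field, no later analysis can separate reporting from occurrence.

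**Working it through.** **Inputs from the protocol.**
- Sample size (8.1): 104 evaluable, 130 included, 1:1. Check: per arm 2 × (1.96 + 0.8416)² × 25² / 14² = 50.06, so 51. The t-test version gives 51.03, rounded up to 52, and 2 × 52 = 104. Then 104 / 0.80 = 130, or 65 per arm.
- Calls (6.1): nurse 1 + 6 = 7; counselor 6; total 13.
- No sample size or power is given for the AE comparison.

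**Assumed inputs (not in the protocol).** True AE incidence p, equal in both arms, and reporting probabilities d1 (Arm 1) and d2 (Arm 2) among affected patients.

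**Formulas.** Recorded proportions: a = p × d1 and b = p × d2. Odds ratio: [b/(1−b)] / [a/(1−a)]. Chance of two-sided significance at 5% with n = 65 per arm: Φ((|b−a| − 1.96 × SE0)/SE1), where SE0 = √(2m(1−m)/n), m = (a+b)/2, and SE1 = √(a(1−a)/n + b(1−b)/n).

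**Worked case.** p = 0.50, d1 = 0.60, d2 = 0.90:
- a = 0.30, b = 0.45, m = 0.375
- OR = (0.45/0.55)/(0.30/0.70) = 1.91
- SE0 = 0.0849, SE1 = 0.0839
- Φ((0.15 − 0.1664)/0.0839) = Φ(−0.196) = 0.42
- Unpooled form: Φ(0.15/0.0839 − 1.96) = Φ(−0.17) = 0.43

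The choice of formula moves the results by about one percentage point.

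| True incidence | Reporting, Arm 1 vs Arm 2 | Recorded | OR | False significance |
|---|---|---|---|---|
| 40% | 70% vs 80% | 28% vs 32% | 1.21 | about 7% |
| 50% | 70% vs 90% | 35% vs 45% | 1.52 | about 21% |
| 60% | 70% vs 90% | 42% vs 54% | 1.62 | about 28% |
| 50% | 60% vs 90% | 30% vs 45% | 1.91 | about 42–43% |
| 80% | 70% vs 90% | 56% vs 72% | 2.02 | about 48% |
| 80% | 50% vs 90% | 40% vs 72% | 3.86 | about 97% |

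**Other direction.** Swapping the reporting rates in the worked case gives 45% vs 30%, OR (0.30/0.70)/(0.45/0.55) = 0.52, with the same chance of significance.

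**Masking.** If true incidence were 60% in Arm 1 and 40% in Arm 2, with reporting of 60% vs 90%, the recorded proportions would be 0.60 × 0.60 = 36% and 0.40 × 0.90 = 36%. A real reduction would disappear.

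**Wording, side by side.** Section 7.3.1 gives a window (the whole period), 8.6.4 gives occasions (scheduled and unscheduled visits), and 8.3.3 and the schedule give one occasion (month 12). No sentence links them. The objective names a count; the endpoint and 8.3.3 name a proportion; 8.6.4 tabulates both. Section 8.6.3 would also call for a month-6 analysis of a dichotomized endpoint that the schedule captures only at month 12.

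**The case against.** The strongest reply is that AE collection is tied to clinic visits. Those visits are the same in both arms, and site staff are meant to be blinded unless the patient reveals the arm (6.4). No section makes the calls an AE source. Bias therefore needs a further step that the protocol does not describe. This stands as far as it goes: the bias is a risk, not a demonstrated effect. A reader might infer that the calls must raise reporting in Arm 2, but the text does not support that, and the direction is open.

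Three other stronger readings should also be set aside.
- **Thirteen extra calls.** Thirteen is Arm 2's scheduled total. Arm 1's technical-support contacts are not stated, so the excess is unknown. Six of the 13 are lifestyle conversations, and the questions on treatment belong to the nurse service.
- **Pure 12-month recall.** Unscheduled visits, whole-period documentation, 24-hour notification and the follow-up of withdrawing patients (5.4) all provide earlier routes. Month 12 is the only scheduled AE assessment, not the only route.
- **An undefined measure.** Every endpoint list names the proportion, so number versus proportion is mostly a wording slip. The timing passages can also largely be reconciled by reading visit 2 as a final check on top of ongoing recording, but the protocol should say so.

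It may also be said that the endpoint is explicitly reported AEs. That is true, but a between-arm comparison invites a causal reading, and unequal prompting undermines it. What remains is unequal contact, spontaneous reporting, and no stated route from calls to the eCRF.

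**Conclusion.** The point holds as a limit on interpretation. As planned, a difference in AE proportions between arms, or the lack of one, could not be attributed to MSP, because the likelihood of reporting may differ between arms in an unknown direction. On assumed values, the chance of a false significant difference at 65 per arm ranges from about 7%, close to the nominal 5%, to about 43%, and beyond that only with large reporting gaps or high incidence. These figures show what could happen; nothing in the protocol fixes the incidence or the reporting rates. The capture and measure wording is a smaller matter of alignment. The comparison concerns a secondary and safety endpoint, so the primary analysis and the sample size are not touched. The change is worth making because it is cheap and cannot be made after data collection.

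**What to change.** 1. Have the blinded study nurse ask one open AE question, in identical words in both arms, at visit 2 and at any early-discontinuation visit. This is in addition to ongoing recording.
2. Add an eCRF field for the source of each AE: visit-2 question, unscheduled visit or support call.
3. Compare arms on all clinic-recorded AEs. List AEs known only through support calls descriptively. Add a sensitivity analysis limited to answers to the visit-2 question. That subset should not be the main comparison, because it would discard AEs from unscheduled visits.
4. State that call-primed recall cannot be excluded when the result is interpreted. A common question lessens unequal elicitation but does not remove that effect.
5. Reconcile 7.3.1, 8.3.3, 8.6.4 and the schedule on when AEs are captured, and name the proportion of patients in both the objective and the endpoint.

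Safety reporting duties stay as they are. The cost is one question, one eCRF field and somewhat more minor AEs to record.
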